17. APPENDICES

Appendix A: ECOG Performance Status Criteria

ECOG Performance Status Scale		Karnofsky Performance Scale			
Grade	Grade Descriptions		Description		
0	Normal activity. Fully active, able to carry on all pre-disease performance without restriction.	100	Normal, no complaints, no evidence of disease.		
0		90	Able to carry on normal activity; minor signs or symptoms of disease.		
1	Symptoms, but ambulatory. Restricted in physically strenuous activity, but ambulatory and able to carry out work of a	80	Normal activity with effort; some signs or symptoms of disease.		
1	light or sedentary nature (e.g., light housework, office work).	70	Cares for self, unable to carry on normal activity or to do active work.		
In bed <50% of the time. Ambulatory and capable of all self-care, but unable to carry		60	Requires occasional assistance, but is able to care for most of his/her needs.		
2	out any work activities. Up and about more than 50% of waking hours.	50	Requires considerable assistance and frequent medical care.		
2	In bed $> 50\%$ of the time. Capable of only		Disabled, requires special care and assistance		
5	more than 50% of waking hours.	30	Severely disabled, hospitalization indicated. Death no imminent.		
1	100% bedridden. Completely disabled. Cannot carry on any self-care. Totally confined to bed or chair.	20	Very sick, hospitalization indicated. Death not imminent.		
4		10	Moribund, fatal processes progressing rapidly.		
5	Dead	0	Dead		

CONFIDENTIAL

Appendix B: New York Heart Association (NYHA) Classification of Cardiac Disease

Objective Assessment Functional Capacity Class Ι Patients with cardiac disease but without resulting limitations of physical No objective evidence of activity. Ordinary physical activity does not cause undue fatigue, cardiovascular disease. palpitation, dyspnea, or anginal pain. Patients with cardiac disease resulting in slight limitation of physical Π Objective evidence of activity. They are comfortable at rest. Ordinary physical activity results in minimal cardiovascular fatigue, palpitation, dyspnea, or anginal pain. disease. III Patients with cardiac disease resulting in marked limitation of physical Objective evidence of activity. They are comfortable at rest. Less than ordinary activity causes moderately severe fatigue, palpitation, dyspnea, or anginal pain. cardiovascular disease. IV Patients with cardiac disease resulting in inability to carry on any physical Objective evidence of activity without discomfort. Symptoms of heart failure or the anginal severe cardiovascular syndrome may be present even at rest. If any physical activity is undertaken, disease. discomfort is increased.

The following table presents the NYHA classification of cardiac disease.

Source: The Criteria Committee of New York Heart Association. Nomenclature and Criteria for Diagnosis of Diseases of the Heart and Great Vessels. 9th Ed. Boston, MA: Little, Brown & Co; 1994:253-256.

CONFIDENTIAL

Appendix C: Guidelines for Female Patients of Childbearing Potential and Fertile Male Patients

Acceptable Contraception Methods:

Women of childbearing potential, defined as all women physiologically capable of becoming pregnant, must use highly effective contraception during the study and for 3 months after stopping treatment.

Highly effective contraception is defined as either:

True Abstinence	When this is in line with the preferred and usual lifestyle of the subject.
	Periodic abstinence (e.g., calendar, ovulation, symptothermal, post-
	ovulation methods) and withdrawal are not acceptable methods of
	contraception.

Sterilization When a woman of childbearing potential has had surgical bilateral oophorectomy (with or without hysterectomy) or tubal ligation at least six weeks prior to study entry. In case of oophorectomy alone, only when the reproductive status of the woman has been confirmed by follow up hormone level assessment.

Male Partner Sterilization When the appropriate post-vasectomy documentation of the absence of sperm in the ejaculate.

Use of a combination of any two of the following (one from a + one from b):

a) Placement of an intrauterine device (IUD) or intrauterine system (IUS)

b) Barrier methods of contraception: Condom or Occlusive cap (diaphragm or cervical/vault caps) with spermicidal foam/gel/film/cream/vaginal suppository.

Fertile male patients, defined as all males physiologically capable of conceiving offspring, with female partners of child-bearing potential must use condoms plus spermicidal agent during the study treatment period and for 3 months after the last dose of study drug, and should not father a child during this period.

Male patients must also refrain from donating sperm during their participation in the study.

The following are acceptable forms of barrier contraception:

• Latex condom, diaphragm or cervical/vault cap when used with spermicidal foam/gel/film/cream/suppository

Unacceptable Contraception Methods: for women of childbearing potential include:

- IUD progesterone T
- Female condom

CONFIDENTIAL

STUDY DRUG(S): CARFILZOMIB AMENDMENT 2 DATE: 25 FEBRUARY 2015

SCRI INNOVATIONS STUDY NUMBER: GI 195

- Natural family planning (rhythm method) or breastfeeding
- Fertility awareness
- Withdrawal
- Cervical shield

Pregnancies

To ensure subject safety, each pregnancy in a subject on study treatment must be reported to the SCRI Innovations Safety Department within 24 hours of learning of its occurrence. The pregnancy should be followed up for 3 months after the termination of the pregnancy to determine outcome, including spontaneous or voluntary termination, details of the birth, and the presence or absence of any birth defects, congenital abnormalities, or maternal and/or new born complications.

Pregnancy should be recorded on a Clinical Study Pregnancy Form and reported by the investigator to **SCRI Innovations Safety Department**. Pregnancy follow-up should be recorded on the same form and should include an assessment of the possible relationship to the study drug of any pregnancy outcome. Any SAE experienced during pregnancy must be reported on the SAE Report Form.

Pregnancy outcomes must be collected for the female partners of any males who took study treatment in this study. Consent to report information regarding these pregnancy outcomes should be obtained from the mother.

Women Not of Childbearing Potential are defined as Follows:

- Women are considered post-menopausal and not of childbearing potential if they have had 12 months of natural (spontaneous) amenorrhea with an appropriate clinical profile (e.g., age appropriate, history of vasomotor symptoms).
- Women who are permanently sterilized (e.g., tubal occlusion, hysterectomy, bilateral salpingectomy, bilateral oophorectomy).
- Women who are >45 years-of-age, not using hormone-replacement therapy and who have experienced total cessation of menses for at least 12 months OR who have a follicle stimulating hormone (FSH) value >40 mIU/mL and an estradiol value <40 pg/mL (140 pmol/L).
- Women who are >45 years-of-age, using hormone-replacement therapy and who have experienced total cessation of menses for at least 1 year OR who have had documented evidence of menopause based on FSH >40 mIU/mL and estradiol <40 pg/mL prior to initiation of hormone-replacement therapy.

CONFIDENTIAL

Appendix D: Schedule of Assessments

		STUDY TREATMENT (Cycles repeated every 28 days)			FOLLOW-UP				
ASSESSMENTS	Pre- Treatment Baseline ^a	Day 1	Day 2	Day 8	Day 9	Day 15	Day 16	End of Study Evaluation ^m	Prior to disease progression ⁿ
Tests and Observations			-	-	-	-			
Informed consent	Х								
Medical history	Х							Х	Х
Physical exam ^b	Х	Х						Х	Х
Vital Signs ^c	Х	Х	Х	Х	Х	Х	Х	Х	
ECOG PS	Х	Х		Х		Х		Х	
12-lead ECG	Х								
ECHO ^d	Х								
Adverse event evaluation		Х	Х	Х	Х	Х	Х	Х	
Concomitant medication review	Х	Х	Х	Х	Х	Х	Х	Х	
Survival status									
Laboratory Assessments	-								•
CBC, 3-part differential, and platelets	Х	Х		Х		Х		Х	Х
CMP ^e	Х	Х		Х		Х		Х	Х
PT, PTT, INR ^f	Х								
Serum or Urine Pregnancy Test ^g	X							Х	
Archival Tumor Tissue Samples	X^h								
Fasting serum chromagranin A ⁱ	X ⁱ	X ⁱ							
24 hour urine for 5-HIAA ^j		Xj							Х
Staging (Every 3 cycles)									
CT Scan chest ^k	Х							Х	X
CT Scan abdomen /pelvis ¹	Х							Х	Х

STUDY DRUG(S): CARFILZOMIB AMENDMENT 2 DATE: 25 FEBRUARY 2015 CONFIDENTIAL SCRI INNOVATIONS STUDY NUMBER: GI 195 VERSION 3.0

Appendix D: Schedule of Assessments (continued)

- a Baseline procedures including medical history, physical examination, peripheral neuropathy assessment, 12-lead ECG, ECOG PS, CBC, CMP, PT/PTT/INR, and serum or urine pregnancy test should be done \leq 7 days prior to initiation of treatment. However, if these initial examinations are obtained within 72 hours of Cycle 1 Day 1 they do not have to be repeated. Scans should be performed \leq 28 days prior to initiation of treatment, to document measurable or evaluable disease.
- b Physical examination will include measurements of height (pre-treatment visit only), weight, and vital signs.
- c Vital signs will include resting heart rate, blood pressure, respiratory rate, and temperature.
- d ECHO with calculated LVEF (repeat if/when clinically indicated). MUGA is acceptable if ECHO is not available.
- e CMP will include measurements of glucose, BUN, creatinine, sodium, potassium, chloride, calcium, CO², ALP, AST, ALT, total bilirubin, total protein, and albumin.
- f If PT/PTT/INR are normal at baseline they do not need to be repeated. Patients requiring the initiation of an anti-coagulation therapy during study treatment should have coagulation tests performed according to standard practice guidelines.
- g Serum or urine pregnancy tests are to be conducted in women of childbearing potential at the beginning of the study and at the end of study visit or 30 days post last dose..
- h If available, archival tissue samples will be requested by study site personnel.
- i Fasting (overnight) serum chromagranin A test will be done during screening and then on Day 1 of each cycle.
- j 24 hour urine for 5-HIAA will be done during screening and then every 3 cycles to assess response.
- k CT scans of the chest \leq 4 weeks prior to initiation of treatment and then every 3 cycles during the treatment and at the end of study visit, if no PD and not done within prior 6 weeks.
- 1 CT scans of the abdomen/pelvis \leq 4 weeks prior to initiation of treatment and then every 3 cycles during the treatment and at the end of study visit.
- m Patients should visit the study center \leq 30 days for end-of-treatment assessments. Patients must be followed for AEs for 30 calendar days after the last dose of study drug.
- n Patients who discontinue study treatment prior to the occurrence of disease progression will be followed every 3 months (±1 month) from the date of last dose of study drug until disease progression. PFS will be evaluated for this trial 6 and 12 months after the last patient is enrolled. No follow up will be done for survival or if the patient starts a subsequent therapy.

STUDY DRUG(S): CARFILZOMIB AMENDMENT 2 DATE: 25 FEBRUARY 2015 CONFIDENTIAL SCRI INNOVATIONS STUDY NUMBER: GI 195 VERSION 3.0

Appendix E: Response Evaluation Criteria in Solid Tumors (RECIST) Version 1.1

Definitions

Response and progression will be evaluated in this study using the Response Evaluation Criteria in Solid Tumors (RECIST) version 1.1 (Eisenhauer et al 2009). Lesions are either measurable or non-measurable using the criteria provided below. The term "evaluable" in reference to measurability will not be used, as it does not provide additional meaning or accuracy.

Baseline Eligibility

Measurable Disease:	Tumor lesions: Must be accurately measured in at least one dimension				
	(longest diameter in the plane of measurement is to be recorded) with				
	10 mm by CT by computerized tomography (CT scan slice thickness)				
	 10 mm caliper measurement by clinical exam (lesions that cannot be accurately measured with calipers should be recorded as non-measurable). 				
	• 20 mm by chest x-ray.				
	Skin lesions: Documentation by color photography, including a ruler to estimate the size of the lesion, is recommended.				
	Malignant lymph nodes: To be considered pathologically enlarged and measurable, a lymph node must be ≥ 15 mm in short axis when assessed by CT scan. At baseline and in follow-up, only the short axis will be measured and followed.				
Non-Measurable Disease:	All other lesions, including small lesions (longest diameter <<10 mm or pathological lymph nodes with \geq 10- to <<15-mm short axis) as well as truly non-measurable lesions. Lesions considered truly non-measurable include: leptomeningeal disease, ascites, pleural or pericardial effusion, inflammatory breast disease, lymphangitic involvement of skin or lung, abdominal masses, abdominal organomegaly identified by physical exam that is not measurable by reproducible imaging techniques.				
Target Lesions:	The most reproducible measurable lesions, up to a maximum of 2 lesions per organ and 5 lesions in total, representative of all involved organs should be identified as target lesions and recorded and measured at baseline.				
	Target lesions should be selected on the basis of their size (lesions with the longest diameter), should be representative of all involved organs, and in addition should be those that lend themselves to reproducible repeated measurements. Pathological nodes which are defined as measurable and that may be identified as target lesions must meet the criterion or a short axis of ≥ 15 mm by CT scan.				
	A sum of the diameters (longest for non-nodal lesions, short axis for nodal lesions) for all target lesions will be calculated and reported as the baseline sum diameters. If lymph nodes are to be included in the sum, then as noted above, only the short axis is added into the sum. The baseline sum diameters will be used as reference to further characterize any objective tumor response.				
Non-Target Lesions:	All other lesions should be identified as non-target lesions at baseline. Measurements of these lesions are not required, but the presence or absence of each should be noted throughout follow-up.				
CONFIDENTIAL					
STUDY DRUG(S): CARFILZOMIB AMENDMENT 2 DATE: 25 FEBRUA	ARY 2015 SCRI INNOVATIONS STUDY NUMBER: GI 195 VERSION 3.0				

Guidelines for Evaluation of Measureable Disease

All measurements should be taken and recorded in metric notation, using a ruler or calipers. All baseline evaluations should be performed as closely as possible to the beginning of treatment, as per protocol screening requirements.

The same method of assessment and the same technique should be used to characterize each identified and reported lesion at baseline and during follow-up. Imaging-based evaluation is preferred to evaluation by clinical examination when both methods have been used to assess the anti-tumor effect of a treatment.

Clinical Lesions:	Clinical lesions will only be considered measurable when they are superficial (e.g., skin nodules and palpable lymph nodes) and ≥ 10 mm in diameter. In the case of skin lesions, documentation by color photography, including a ruler to estimate the size of the lesion, is recommended.
Chest X-ray:	Lesions on chest X-ray are acceptable as measurable lesions when they are clearly defined and surrounded by aerated lung. However, a CT scan is preferable.
Conventional CT and MRI:	CT, MRI: CT is the best currently available and reproducible method to measure lesions selected for response assessment. This guideline has defined measurability of lesions on CT scan based on the assumption that CT slice thickness is 5mm or less. When CT scans have slice thickness greater than 5 mm, the minimum size for a measurable lesion should be twice the slice thickness. MRI is also acceptable in certain situations (e.g. for body scans).
Ultrasound:	When the primary study endpoint is objective response, ultrasound should not be used to measure tumor lesions. It is, however, a possible alternative to clinical measurements of superficial palpable lymph nodes, subcutaneous lesions, and thyroid nodules. Ultrasound may also be useful to confirm the complete disappearance of superficial lesions usually assessed by clinical examination.
Endoscopy and Laparoscopy:	Use of endoscopy and laparoscopy for objective tumor evaluation has not yet been fully and widely validated. Therefore, use of these techniques for objective tumor response should be restricted to validation purposes in specialized centers. Such techniques can be useful in confirming complete pathological response when biopsies are obtained.
Tumor Markers:	Tumor markers alone cannot be used to assess response. If markers are initially above the upper limit of normal, they must normalize for a subject to be considered in complete clinical response when all lesions have disappeared.
Cytology and Histology:	Cytology and histology can be used to differentiate between partial response (PR) and complete response (CR) in rare cases (e.g., after treatment to differentiate between residual benign lesions and residual malignant lesions in tumor types such as germ cell tumors).

CONFIDENTIAL

STUDY DRUG(S): CARFILZOMIB AMENDMENT 2 DATE: 25 FEBRUARY 2015

Response Criteria

Evaluation of Target Lesions

Complete Response (CR):	Disappearance of all target lesions.		
Partial Response (PR):	At least a 30% decrease in the sum of diameters of target lesions, taking as reference the baseline sum diameters		
Stable Disease (SD):	Neither sufficient shrinkage to qualify for PR nor sufficient increase to qualify for PD, taking as reference the smallest (nadir) sum of diameters since the treatment started.		
Progressive Disease (PD):	At least a 20% increase in the sum of the diameters of target lesions, taking as reference the smallest (nadir) sum since the treatment started, or the appearance of one or more new lesions. Requires not only 20% increase, but absolute increase of a minimum of 5 mm over sum.		

Evaluation of Non-Target Lesions

Complete Response (CR):	Disappearance of all non-target lesions and normalization of tumor markers. All lymph nodes must be non-pathological in size (<<10 mm short axis).		
Stable Disease (SD):	Persistence of one or more non-target lesions and/or persistence of tumor marker level above the normal limits.		
Progressive Disease (PD):	Appearance of one or more new lesions and/or unequivocal progression of existing non-target lesions. When the subject also has measurable disease, to achieve "unequivocal progression" on the basis of the non-target disease, there must be an overall level of substantial worsening in non-target disease such that, even in presence of SD or PR in the target disease, the overall tumor burden has increased sufficiently to merit discontinuation of therapy.		

Evaluation of Best Overall Response

The best overall response is the best response recorded from the start of the treatment until disease progression/recurrence (taking as reference for PD the smallest measurements recorded since the treatment started). In general, the subject's best response assignment will depend on the achievement of both measurement and confirmation criteria.

Confirmation of response (by repeat scans after 4 weeks or as specified in the protocol) is required for studies in which response rate is the primary endpoint, but is not required in randomized studies or studies with primary survival endpoints (i.e., where response is not a primary endpoint).

CONFIDENTIAL

Target Lesions	Non-Target Lesions	New Lesions	Overall Response	
CR	CR	NO	CR	
CR	SD	NO	PR	
CR	NE	NO	PR	
PR	SD OR NE	NO	PR	
SD	SD OR NE	NO	SD	
PD	ANY	YES OR NO	PD	
ANY	PD	YES OR NO	PD	
ANY	ANY	YES	PD	

In some circumstances, it may be difficult to distinguish residual disease from normal tissue. When the evaluation of a CR depends upon this determination, it is recommended that the residual lesion be investigated by fine needle aspirate or biopsy to confirm the CR status.

When nodal disease is included in the sum of target lesions, and the nodes decrease to "normal" size (<<10 mm), they may still have a measurement reported on scans. This measurement should be recorded even though the nodes are normal in order not to overstate progression, should it be based on increase in size of the nodes. As noted earlier, this means that subjects with CR may not have a total sum of "zero" on the eCRF.

CONFIDENTIAL

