5.2 Treatment Duration

Patients will be evaluated for toxicity at the start of each cycle. Every 3 cycles, restaging will occur with imaging, laboratory chemistries, and tumor markers as defined in Appendix D. Patients will continue on treatment until progression as defined in Appendix E or intolerance to side effects.

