7. STUDY ASSESSMENTS AND EVALUATIONS

7.1 Overview

All patients should visit the study center on the days specified within this protocol. The complete Schedule of Assessments for this study is shown in Appendix D. The baseline physical examination, medical history, ECOG PS, 12-lead electrocardiogram (ECG), complete blood counts (CBC), differential and platelets, complete metabolic profile (CMP), prothrombin/partial thromboplastin time/international normalization ratio (PT/PTT/INR), and serum pregnancy test should be done \leq 7 days prior to initiation of treatment. If urine pregnancy test is being done, it must be performed within 72 hours of Cycle 1 Day 1. However, if these initial examinations are obtained within 72 hours of Cycle 1 Day 1 they do not have to be repeated on Cycle 1 Day 1. CT scans and LVEF assessment should be performed \leq 28 days prior to initiation of treatment, as should tumor markers, if appropriate.

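### Appendix E does not say that the baseline sum counts in the reference for progression, so target-lesion progression can be called late, and never early, in PFS and CBR

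*Combined protocol and SAP*

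**What the plan says.** Appendix E gives two reference points for target lesions. Partial response is judged "taking as reference the baseline sum diameters". Progressive disease is judged "taking as reference the smallest (nadir) sum since the treatment started, or the appearance of one or more new lesions", with a further condition: "Requires not only 20% increase, but absolute increase of a minimum of 5 mm over sum". The stable-disease row uses the same on-treatment nadir as the progression row. The paragraph on best overall response repeats it: "taking as reference for PD the smallest measurements recorded since the treatment started".

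The baseline scan comes before treatment. Section 7.1 places CT scans up to "28 days prior to initiation of treatment, as should tumor markers, if appropriate", and Section 7.2 agrees. Scans then follow every 3 cycles of 28 days (Sections 5 and 7.4).

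Appendix E is the working definition. Section 5.2 states: "Patients will continue on treatment until progression as defined in Appendix E or intolerance to side effects". Section 10.4.1 dates PFS from Day 1 to RECIST v1.1 progression or death on study. It counts CBR as CR, PR, or stable disease for at least 6 cycles.

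**The concern.** The appendix names the baseline sum for response and a different reference for progression, and never links the two. A reader who applies the wording takes the smallest sum measured after treatment began. For a tumour that grows from the start, that sum is the week-12 value, which already contains 12 weeks of growth. The 20% threshold is then set from too high a point.

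Any error runs one way, toward longer PFS and more stable disease, and a single-arm trial has no control group in which the same error would cancel. Slow growth is also the setting where it matters most: Section 1.1 describes GI carcinoids as generally slow-growing, and entry is limited to well-to-moderately differentiated disease.

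**Working it through.** **1. The plan's own figure.** Section 10.2 states type I error 0.05 and power 80% for 23 then 56 patients (stop at 1 or fewer responses, reject at 6 or more). With Bin(x; 23, p) the probability of x responses in stage 1, the rejection probability is the sum over x = 2 to 23 of Bin(x; 23, p) × P(at least 6 − x responses in 33). This gives 0.04996 at p = 0.05 and 0.8003 at p = 0.15, so the figure reproduces. It depends on ORR only, and PR is measured from baseline, so the progression reference does not enter.

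**2. Scan interval.** 3 × 28 = 84 days, or 12 weeks. At 30.44 days per month, this is 2.76 months.

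**3. Direction.** Let m be the reference sum. Target-lesion progression needs a sum of at least 1.2m and at least m + 5 mm. Both limits rise with m. Removing baseline from the set can only raise m or leave it unchanged. Progression is therefore called later or at the same scan, never earlier.

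**4. Example: 15% growth per 12 weeks, baseline 100 mm.**

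| Week | Sum (mm) | Against baseline | Against smallest earlier on-treatment sum |
|---|---|---|---|
| 12 | 115.0 | +15% | none exists |
| 24 | 132.3 | +32%: PD | +15%: not PD |
| 36 | 152.1 | +52% | +32%: PD |

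**5. Other paths.** Growth rates are assumptions, since the documents give none. The steady-growth results are the same for baseline sums of 50 and 100 mm.

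| Path | PD scan, baseline included | PD scan, on-treatment sums only |
|---|---|---|
| Constant 5% per scan | 4 | 5 |
| Constant 8% | 3 | 4 |
| Constant 10% or 15% | 2 | 3 |
| Constant 20% to 50% | 1 | 2 |
| Linear 10% of baseline per scan | 2 | 4 |
| Linear 15% of baseline per scan | 2 | 3 |
| 100, 125, then flat | 1 | never |
| 100, 95, 100, 110, 120 | 4 | 4 |
| 100, 80, 85, 97 | 3 | 3 |

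**6. Who changes category for CBR.** The 6-cycle scan is scan 2. With baseline included, constant growth g per scan is PD by then if (1 + g)² ≥ 1.2, so g ≥ √1.2 − 1 = 9.5%. Against the week-12 sum it needs 1 + g ≥ 1.2, so g ≥ 20%. Tumours between 9.5% and 20% per scan move from progression to stable disease at 6 cycles. At 20% or more, the strictly literal rule moves PD from week 12 to week 24, and CBR changes only if stable disease is counted up to the PD date.

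**7. Illustration of size.** Let T be the time to 20% growth over baseline. Assume steady exponential growth, with T exponentially distributed with median M months. For M, borrow the comparator-arm median PFS values in Section 1.2: 4.6, 5.5 and 11.3 months. No PD at week 24 then has probability 2^(−5.52/M) with baseline included and 2^(−2.76/M) without. If only a fraction f of progressions is affected, the result is the first value plus f times the difference.

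| M (months) | Baseline included | f = 0.3 | f = 0.5 | f = 1 |
|---|---|---|---|---|
| 4.6 | 44% | 50% | 55% | 66% |
| 5.5 | 50% | 56% | 60% | 71% |
| 11.3 | 71% | 75% | 78% | 84% |

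**The case against.** The text does not exclude baseline. Appendix E opens with "Response and progression will be evaluated in this study using the Response Evaluation Criteria in Solid Tumors (RECIST) version 1.1", and PFS is defined by that standard. It also says "The baseline sum diameters will be used as reference to further characterize any objective tumor response". The strictly literal reading defeats itself at week 12: no earlier on-treatment sum exists, so neither stable nor progressive target disease could be assigned, yet Section 7.4 expects both to be recognised after the first 3 cycles. A sensible assessor would use baseline there.

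That argument stands for week 12. It does not carry to week 24, when an on-treatment sum exists and the wording points to it. The example in the working uses baseline at week 12 without harm (15% is not PD) and still loses 12 weeks. A path of 100, 115, 125, then flat is 25% above baseline at week 24, but 125/115 is only 8.7% above the week-12 sum, so it would never be called. The sentence on the baseline sum concerns response and does not mention progression. The sections that cite RECIST v1.1 send the reader to Appendix E, which is the only statement of the criteria in the plan.

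The objection on size also stands. Median PFS is not time to 20% target growth, and using it as such is a modelling choice. The f = 1 column needs every progression to be target growth from the outset, and every assessor to follow the wording.

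**Conclusion.** The gap in wording is real, and any error it causes favours the drug. Target-lesion progression can be called later than it would be against baseline, by one scan under constant percentage growth and by two or without limit on some other paths. The delay is zero where the first on-treatment sum is at or below baseline. PFS and CBR can be biased upward, with CBR affected mainly for steady growth of about 9.5–20% per scan. The size is not known. The f = 0.5 figures illustrate it under the stated assumptions and do not estimate it.

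The documents do not support three stronger readings that a reader might infer:

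- **That every progression is recorded one scan late, or that PFS and CBR are shown to be inflated.** Baseline is left unmentioned, not ruled out. Progression by new lesions or non-target disease, and death on study, need no target-lesion nadir.
- **That median PFS shifts by a full scan interval.** This follows only if all progressions are affected, on a 12-week grid.
- **That the primary result is at risk.** PR uses baseline, and no stopping rule or test uses PFS or CBR. The overall-response table does lack rows for target PR with non-target CR, target SD with non-target CR, and no non-target lesions. An analyst would fill these sensibly from the PR definition, and nothing suggests that a responder would be lost.

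Severity is minor to moderate: worth correcting, but not a condition for the trial to proceed.

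**What to change.** In the progressive-disease and stable-disease rows of Appendix E, and in the paragraph on best overall response, state that the reference is the smallest sum of diameters recorded at any assessment, including baseline. Use the same rule in the programmed derivation of PFS and CBR. Section 5.2 ties treatment duration to the Appendix E definition, so the sponsor should confirm that the two remain consistent after the change.

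Optionally, add the missing rows to the overall-response table: target PR with non-target CR is PR, target SD with non-target CR is SD, and with no non-target lesions the overall response follows the target response unless a new lesion appears.

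The cost is a few words. Sample size, visits and the ORR decision rule do not change. PFS and CBR may come out slightly less favourable.
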